2.1 Trial objectives

We were able to demonstrate that treatment of septic mice with the ketone ester 3HHB improved muscle weakness. In order to study this effect in a randomized clinical trial in critically ill patients, we first want to determine a dose of 3HHB that effectively and safely increases plasma 3-hydroxybutyrate concentrations in adult critically ill patients.

To this purpose, we want to test fixed doses of 25 g, 50 g and 75 g of 3HHB in order to reach an increase of 0.22 mmol/l plasma 3-hydroxybutyrate, as was observed with the effective dose of 3HHB in earlier mice studies [13]. The fixed doses of 25 g, 50 g and 75 g that will be tested are based on the human equivalent (0.6 g/kg/day) of the effective and non-toxic dose in rodents (7 g/kg/day) [16]. Sustained ketosis through oral ingestion of the ketone ester 3HHB has previously been shown to be safe in healthy adults, tested at doses between 0.140 and 2.142 g/kg/day for up to 28 days [10, 11, 15].

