We will first perform this trial with a 25 g dose of 3HHB divided over 6 boluses. The density of 3HHB is 1.07 g/ml, 25 g has a volume of 23.4 ml, so each bolus consist of 3.9 ml 3HHB. Next, we will assess the primary and secondary endpoints in this cohort of patients. If the dose of 25 g is found safe but ineffective for increasing plasma 3-hydroxybutyrate at least with 0.22 mmol/l, a second cohort of patients will be tested with the same cross-over study design but with a higher 3HHB dose (50 g of 3HHB, divided over 6 boluses of 7,8 ml). If this dose is again safe but ineffective, a third cohort of patients will be tested with the same cross-over study design with an increased dose of 75 g of 3HHB, divided over 6 doses of 11.7ml. For each cohort of patients tested (cohort I to test 25 g, cohort 2 to test 50 g and cohort 3 to test 75 g),

16 patients will be included. If a patient is not able to complete the 48h study period (e.g. due to consent withdrawal or due to unplanned surgery or other procedures) and this is not related to safety concerns that are directly attributed to the intervention, an extra patient will be included in order not to compromize the statistical power of the study.

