7.1 Sample Size

The study is powered to detect a 0.22 mM within-patient increase in plasma 3HB with 95% certainty, 80% power, calculated with a paired t-test. The anticipated effect size is 0.786 given that patients not treated with ketone esters have a mean difference of 0.001mM between intervention day I and 2 with a SD of 0.28mM (based on prior data from ICU patients) and the anticipated required increase with the administration of ketone esters is 0.22mM (which was the effective increase in the mice studies). If the lower limit of the 95% confidence interval is not above 0.22mM increase, a higher dose will be tested.

Approximately 160 participants will be screened to achieve 16 participants completing the 48h study period or an estimated total of 8 evaluable participants per treatment group.

The screening will be repeated for each dose study. In total a maximum of approximately 480 patients will be screened and a maximum of 3x 16 patients completing the 48h study period will be included.

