7.2 Statistical Analysis

For each patient, and for each study day, maximum concentration, time to reach maximum concentration, delta Max (difference between maxium concentration and baseline concentration), area under the curve, elimination rate and elimination half life will be calculated for 3HBB and its metabolites 3-hydroxybutyrate and 1,3-butanediol. Delta Max of 3-hydroxybutyrate and time within range (plasma 3-hydroxybutyrate 0.22mmol/l above baseline value) will be calculated as primary outcome variables. For blood lipid parameters, maximum concentration, time to reach maximum concentration, delta Max (difference between maximum concentration and baseline concentration), and area under the curve will be calculated. Data will be compared with paired t-tests after transforming the data to near-normally distributed values if needed. If the latter is not possible, non-parametrical tests will be used. Within the crossover design, each patient thus serves as his/her own control.

To investigate whether the order of administration of placebo and 3HHB affected the response, the delta Max of the placebo day and the 3HHB day will be assessed with a repeated measures ANOVA in which the grouping variable will be randomization (placebo/3HHB or 3HHB/placebo) and time is the difference between test day I and test day 2.If more than one dose will be tested, parameters will also be compared between doses. These data will be compared with standard t-tests after transforming the data to near-normally distributed values if needed. If the latter is not possible, non-parametrical tests will be used. P-values will be considered significant when at or below 0.05 without correction for multiple testing. If a higher dose reached a significant increase in the paired analysis, and also compared to the lower dose, this will further strengthen the conclusion that the lower dose was ineffective while the higher dose was effective. If the higher dose does not reach a statistical difference from the lower dose this might suggest that the lower dose already created a small, but non-statistical increase which was not picked-up in the paired analysis.

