8.2 Study specific data handling information

The data will be stored in a validated Filemaker database with password protection and complete audit trail. Beside account access control on system level by the Active Directory which governs access to all clinical UZ- data, a secured, controlled and restricted role-based user access on file level will be implemented. In the Filemaker® application export and printing privileges can be restricted to a certain role since version 10.

For this project export data export privileges will only be granted to the database administrators. The database will be stored on the central FilemakerPro servers which are managed, maintained and backed up by the UZ Leuven IT department according to the central IT policies (at least I daily backup on mirrored servers).

The following data will be collected in the pseudonymized (e)CRF :

- Patient study number
- Informed consent, date of IC, type of IC (patient or legal representative)
- Age
- Sex
- ICU admission date and time
- Height, weight and body mass index (BMI)
- Medical history (diabetes, malignancy, renal replacement therapy, Charlson comorbidity index)
- Baseline characteristics including reason for ICU admission and APACHE II score

- Clinical characterterics from ICU admission until discharge including hemodynamic and respiratory status, renal function, liver function, SOFA score and infections

- ICU length of stay
- ICU mortality

- All medications received by the patients on the ICU before the intervention and on the intervention days will be registered

- Parenteral nutrition (kilocalories, amino acids, lipids and carbohydrates cumulatively administered during intervention window and 1 day prior

- Enteral nutrition (kilocalories, amino acids, lipids and carbohydrates cumulatively administered during intervention window and I day prior

-Results from the routine blood gas analyses on the clinical samples will be collected

- Intervention related parameters:

- Start- and stop date and time of first intervention day
- Start- and stop date and time of second intervention day
- Dose of IMP
- Amount of cycles of IMP administration
- Blood glucose values and ketone values measured at 4h intervals

- Blood 3HHB + metabolites values (3-hydroxybutyrate and 1,3-butanediol) measured in collected blood samples

- Blood lipid values (HDL, LDL, total cholesterol, triglycerides and free fatty acids) measured in collected blood samples

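### The between-dose comparison in section 7.2 is an unadjusted t-test between sequential, non-randomised fixed-gram cohorts, although body weight is already recorded and could be a covariate

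*Protocol*

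**What the plan says.** Section 7.2 fixes the between-dose test. If a second or third dose is studied, "parameters will also be compared between doses. These data will be compared with standard t-tests", after transformation where needed and with a non-parametric test as fallback. No covariate is named. On the threshold it says "P-values will be considered significant when at or below 0.05 without correction for multiple testing".

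The same section says how each result will be read. If the higher dose is significant in its paired analysis and also against the lower dose, "this will further strengthen the conclusion that the lower dose was ineffective while the higher dose was effective". The opposite case, beginning "If the higher dose does not reach a statistical difference from the lower dose", is taken as a possible sign that the lower dose already had a small effect.

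Other sections set the context:
- Section 2.1: "we want to test fixed doses of 25 g, 50 g and 75 g of 3HHB". These amounts are derived from a per-kg figure, a human equivalent of 0.6 g/kg/day.
- Section 2.4: randomisation covers only the order of 3HHB and placebo within a patient. If 25 g is safe but raises ketones too little, "a second cohort of patients will be tested with the same cross-over study design" at the higher dose. Section 7.1 repeats screening for each dose.
- Section 3.2: BMI below 20 is excluded, with no upper limit.
- Section 8.2: height, weight and BMI are in the eCRF.
- Section 7.1, escalation: "If the lower limit of the 95% confidence interval is not above 0.22mM increase, a higher dose will be tested".

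**The concern.** Each patient is their own control in the paired analysis, but not in the comparison between doses. That comparison sets 16 patients from one period against 16 others from a later period, and nobody is randomised to dose. A fixed gram dose also gives a light patient more per kg than a heavy one. If 3-hydroxybutyrate response depends on g/kg, weight adds variation to the t-test. A systematic difference in weight between cohorts would go straight into the dose contrast.

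Section 7.2 attaches an interpretation to significance and to non-significance, so the precision and comparability of a small test affect how the lower dose is described. The variable that could help is already collected but is not used here.

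**Working it through.** **The plan's own figure.** Section 7.1 sizes each cohort for the paired test. With d = 0.22/0.28 = 0.786, two-sided alpha 0.05 (sidedness assumed) and 80% power, the exact paired t-test needs 14.7, so 15 patients; 16 gives 83.6%. The stated 16 is reproduced, with rounding to 8 per sequence.

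That number was not chosen for the between-dose test. At 16 versus 16, with SD 0.28 mM assumed in each cohort, an independent t-test has about 58% power for a 0.22 mM difference. It would need 27 per cohort for 80%.

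**Exposure per kg (dose divided by an assumed weight).**

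| Weight | 25 g | 50 g | 75 g |
|---|---|---|---|
| 60 kg | 0.42 | 0.83 | 1.25 |
| 80 kg | 0.31 | 0.62 | 0.94 |
| 100 kg | 0.25 | 0.50 | 0.75 |

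A 100 kg patient on 75 g (0.75 g/kg) receives less per kg than a 60 kg patient on 50 g (0.83 g/kg).

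**Simulation.** Two-sample t-test (30 df) against linear regression on dose and body weight (29 df), 16 per cohort, two-sided 0.05, 40,000 cohort pairs per scenario. Assumed, because the protocol gives neither: log-normal weight with mean 80 kg and SD 15 or 20 kg, and delta Max proportional to g/kg. Two error models were used:
- Additive: delta Max = 0.22 × (dose/25) × (80/weight) + e, with SD(e) = 0.28 mM. This borrows the section 7.1 SD, which describes the day-to-day difference in patients not given ketone esters.
- Log: log(delta Max) = log(dose) − log(weight) + e, with SD(e) = √log(1 + CV²) and CV 40% as the central case.

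Power with equal mean weights, unadjusted → adjusted:

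| Model | Contrast | Weight SD 15 | Weight SD 20 |
|---|---|---|---|
| Additive | 50 vs 25 g | 58 → 59% | 58 → 60% |
| Additive | 75 vs 50 g | 55 → 59% | 53 → 60% |
| Log, CV 40% | 50 vs 25 g | about 99% → nearly 100% | about 99% → nearly 100% |
| Log, CV 40% | 75 vs 50 g | 74 → 80% | 68 → 80% |

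So the gain is about 0 to 2 points (50 vs 25 g) and 4 to 7 points (75 vs 50 g) under the additive model. Under the log model it is 1 point or less and about 7 to 12 points (unrounded 73.6 → 80.3 and 68.4 → 80.5). With equal mean weights and no dose difference, both tests reject 4.8 to 5.2% of the time.

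**If mean weights differ by 10 kg (75 and 85 kg).** On the log scale the t-test estimates the dose ratio times the inverse weight ratio. For 75 vs 50 g the true ratio is 1.5.
- Higher-dose cohort heavier: 1.5 × 75/85 = 1.32, which is 12% low (1.32/1.5 = 0.88). The adjusted estimate is 1.49. At CV 40%, power is 42% unadjusted against 75% adjusted (weight SD 15).
- Higher-dose cohort lighter: 1.5 × 85/75 = 1.70 by hand and 1.71 simulated, which is 14% high (1.71/1.5 = 1.14). The adjusted estimate is 1.51.
- No dose difference, weight SD 15: the t-test rejects about 9% (additive, both cohorts at 50 g) to 13% (log, CV 40%). The adjusted test rejects about 5%.

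**If weight has no effect.** With equal mean weights (log model, weight SD 15, 75 vs 50 g), power goes from 82.0 to 80.7% at CV 40% and from 64.9 to 63.4% at CV 50%, a cost of about 1 to 1.5 points. If mean weights differ by 10 kg, dose and weight are correlated and the cost reaches about 6 points.

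**The case against.** The strongest case against is that little depends on this test. It runs only if a second cohort opens, and section 7.2 gives it a supporting role in cautious words. The objective is a fixed gram dose that works in this population, so weight variation belongs to the target and an unadjusted comparison of gram doses is legitimate. For 50 versus 25 g, the first between-dose comparison that could arise, adjustment gains almost nothing under either error model. Even with a 10 kg heavier 50 g cohort, the log model at CV 40% leaves the t-test 95% power (weight SD 15) or 92% (SD 20). Weight is also only one recorded covariate; feeding state and illness severity differ between patients too. All of this stands, and it keeps the point small.

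The statistical analysis plan, which is not shown, is a weaker defence. The protocol itself names the test and says how both results will be read.

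Two stronger readings may tempt a reader:
- **That the between-dose result is biased by weight.** Chance imbalance costs precision but does not bias the test. Bias needs a systematic shift, and the document gives no specific reason to expect one: one centre, the same eligibility criteria, and an estimated 2 to 4 month screening period per dose. Ten kg is 1.9 standard errors of the difference in mean weight at SD 15 (15 × √(2/16) = 5.3 kg) and 1.4 at SD 20 (7.1 kg).
- **That dose selection is compromised.** The paired analysis and the confidence-interval rule in section 7.1 do not use this test.

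**Conclusion.** The point holds as a minor, inexpensive improvement to a conditional, supportive analysis. The textual facts are clear: an unadjusted test, sequential cohorts not randomised to dose, fixed gram doses, and weight recorded but unused in this comparison. The benefit is less certain. It depends on response following g/kg, on an assumed weight distribution, and on the error model, and it lies mainly in the 75 versus 50 g contrast, which arises only if both lower doses fall short. The protection against a 10 kg shift is real under those assumptions, but the shift itself is hypothetical. It is also unstated whether the compared parameters are 3HHB-day values or differences from placebo; taking differences would not remove the variation in g/kg.

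**What to change.** In section 7.2, replace the between-dose t-test for delta Max of 3-hydroxybutyrate with wording such as: *Delta Max will be compared between doses by linear regression on dose level with body weight as covariate, on the planned transformed scale. The comparison is non-randomised and supportive. If no suitable transformation is found, the planned non-parametric test will be used and labelled unadjusted.*

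Use body weight, not g/kg, as the covariate: g/kg contains the dose and would adjust away the effect being estimated. Doses, the paired primary analysis and the escalation rule stay as they are.

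The cost is a few sentences, one model term and one degree of freedom, with no new data or patients, plus the loss of power shown above if weight turns out not to matter. Adjustment does not remove other differences between the cohorts, such as calendar time or case mix. Nor does it remove the selection from testing a higher dose only after the lower one was judged ineffective. The non-randomised label is therefore needed with or without the covariate.

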The study setup is designed and will continue until 16 participants per tested dose completed the 48h study period. This is the primary analysis (per-protocol-analysis). Data from patients with a shorter study period will be analysed in as a sensitivity analysis to confirm those partial results are in line with the primary data set. Imputation of missing data would not be accurate due to the small data set.

8 Data handling

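### Section 7.2 pre-specifies unsound readings of both outcomes of the supplementary comparison between sequential dose cohorts; escalation is unaffected, but the reported verdict on a dose could be wrong

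*Protocol*

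**What the plan says.** Protocol section 7.1 sizes each cohort for a within-patient paired t-test: 0.22 mM, SD 0.28 mM, 80% power, 16 completers. The SD comes from earlier ICU patients not given ketone esters and describes the difference between two days. Section 7.1 also sets the escalation rule: a higher dose is tested unless the lower 95% confidence limit for the increase lies above 0.22 mM. Under section 2.4 the dose cohorts are enrolled one after another. Randomisation (sections 2.4 and 4.3) covers the order of 3HHB and placebo within a patient, not the dose.

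Section 7.2 then adds: "If more than one dose will be tested, parameters will also be compared between doses". The method is unpaired: "These data will be compared with standard t-tests after transforming the data to near-normally distributed values if needed". The threshold is nominal: "P-values will be considered significant when at or below 0.05 without correction for multiple testing". No power is given for this comparison.

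Two sentences interpret it in advance. If the higher dose is significant in its paired analysis and also against the lower dose, "this will further strengthen the conclusion that the lower dose was ineffective while the higher dose was effective". For the other outcome: "If the higher dose does not reach a statistical difference from the lower dose this might suggest that the lower dose already created" a small, non-significant increase that the paired analysis did not detect.

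**The concern.** Both sentences draw a conclusion about the lower dose from a comparison that cannot supply it.

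- **Significant difference.** The question for a dose is whether its own increase over placebo reaches 0.22 mM. That a larger dose gives a larger increase is expected under any dose-response and does not place the lower dose below 0.22 mM. The lower dose may have led to escalation only because its confidence interval was too wide to clear the limit.
- **Non-significant difference.** With 16 per cohort, low power is an obvious alternative explanation, and the text does not mention it. An inert lower dose can easily produce the same result.

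The cohorts are also consecutive and not randomised to dose, so case mix and calendar time are confounded with dose in either direction.

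The trial exists to identify a dose for later work (section 2.1). A report that followed these sentences could call an active dose ineffective, or suggest activity for an inert one.

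**Working it through.** **Inputs.** From section 7.1: target 0.22 mM, SD of the within-patient difference 0.28 mM. From sections 7.1 and 7.2: 16 completers per dose. From section 7.2: significance at 0.05, taken here as two-sided.

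**1. The plan's own figure.** Effect size 0.22/0.28 = 0.786. An exact paired t-test needs n = 14.7, so 15, for 80% power. With 16 the power is 83.6%. The stated 16 is adequate for the within-cohort test.

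**2. Power of the between-dose test, placebo-corrected variable.** Assume that SD 0.28 mM applies to the 3HHB-minus-placebo difference in both cohorts.

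- Standard error of the difference = 0.28 × √(2/16) = 0.099 mM.
- Noncentrality for a true gap of 0.22 mM = 0.22/0.099 = 2.22, with 30 df and critical t = 2.042.
- Power = 57.6%.
- Gap detectable with 80% power: 0.287 mM. Cohort size for 80% power at 0.22 mM: 27.

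| True gap between doses (mM) | Power |
|---|---|
| 0.05 | 8% |
| 0.11 | 19% |
| 0.15 | 31% |
| 0.22 | 58% |
| 0.30 | 83% |

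If the SD under treatment were 0.35 mM, power at 0.22 mM would fall to 41%.

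**3. The same test on raw 3HHB-day delta Max.** With equal variance on both days and within-patient correlation ρ (assumed; the protocol gives none), the single-day SD is 0.28/√(2(1−ρ)).

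| ρ | SD (mM) | Power at 0.22 mM |
|---|---|---|
| 0 | 0.198 | 86% |
| 0.5 | 0.280 | 58% |
| 0.75 | 0.396 | 33% |

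**4. Non-significance when the lower dose is inert.** Simulation with normal data and SD 0.28 mM, lower dose adding 0, higher dose adding 0.22 mM: the between-dose test is non-significant in 42% of trials. Among trials with a non-significant paired test at the lower dose and a significant one at the higher, it is still non-significant in about a third. In these trials the second sentence would credit a possible effect to a dose that has none.

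**5. Significance when both doses exceed the target.** The half-width of a cohort's 95% CI is 2.131 × 0.28/√16 = 0.149 mM. The observed mean must therefore exceed about 0.22 + 0.149 = 0.369 mM to avoid escalation. Take illustrative true increases of 0.30 and 0.60 mM (assumed, both above target), SD 0.28 mM:

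- The lower dose fails the confidence-limit rule, and escalation follows, in 81% of trials.
- In about 90% of those, the higher dose is significant in its paired test and beats the lower dose, so the condition of the first sentence is met.
- In 97% of the escalated trials, the lower dose itself has a significant paired increase.

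The first sentence would then reinforce a false statement about the lower dose.

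**The case against.** **The comparison decides nothing.** This stands. Escalation depends on each cohort's own confidence limit, and section 7.2 presents the between-dose test as an addition. A reader might infer that the dose-finding conclusion rests on it; sections 2.4 and 7.1 show otherwise.

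**58% is not a property of the plan.** This also stands. It uses an SD from untreated patients and a gap of 0.22 mM between doses, whereas the protocol uses 0.22 mM as a within-patient increase. It must be stated with both conditions and with the 33% to 86% range.

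**The wording is cautious, and non-significance carries some information.** Partly true. The second sentence is hedged. With the higher dose at 0.22 mM, the between-dose test is non-significant in about 42% of trials if the lower dose adds nothing and about 81% if it adds 0.11 mM, roughly a twofold ratio. That is weak evidence, and the text offers it without naming low power as the rival explanation. The first sentence says outright that the conclusion will be strengthened.

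**The 0.30 and 0.60 mM example is the reviewer's and has good power.** True: the gap of 0.30 mM has 83% power. If ineffective meant a non-significant paired test, the pattern of lower dose non-significant and higher dose significant would arise in only about 2% of such trials. But under sections 2.4 and 7.1 a dose counts as ineffective when it fails the 0.22 mM criterion, and on that reading the example applies. It shows an error of logic that more power would not cure.

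**Sequential cohorts are openly described, and the exact variable can be left to a SAP.** Fair. Neither is a defect by itself. They matter because the protocol attaches inferences to the comparison.

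**Conclusion.** The point holds as one about interpretation. Section 7.2 fixes in advance two readings of a supplementary, non-randomised comparison, and neither is sound. A higher dose beating a lower one says nothing about the lower dose against 0.22 mM. This is a matter of logic and needs no assumption about the SD. A non-significant difference does not by itself suggest a small lower-dose effect, because the comparison was not sized. Power is about 58% for a 0.22 mM gap if SD 0.28 mM applies to the 3HHB-minus-placebo difference, and about 33% to 86% for raw 3HHB-day delta Max with assumed correlations of 0.75 to 0.

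The simulated percentages further assume normal data and equal SDs in both cohorts. The true effects are illustrative, since the protocol gives no expected increase by dose.

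Nothing here shows that the within-cohort sample size is too small for its paired test or that escalation would go wrong because of this comparison. What is at risk is the reported conclusion on each dose.

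**What to change.** In section 7.2:

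1. Delete the two sentences that interpret a significant and a non-significant between-dose result.
2. State that the efficacy of each dose is concluded only from the confidence interval of its own placebo-controlled within-patient comparison.
3. State that doses are compared on the within-patient 3HHB-minus-placebo difference in delta Max, reported as an estimate with its 95% CI.
4. Label this comparison descriptive, because the cohorts are sequential and patients are not randomised to dose.

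The cost is protocol wording only: no extra patients, samples or visits, and no change to the escalation rule.

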4.4 Premature discontinuation of Trial treatment

Participants may voluntarily discontinue from Trial treatment and/or prematurely end their participation in the Trial for any reason at any time. In such case the Investigator will make a reasonable effort to document the primary reason for this decision.

The Investigator may also decide at any time during the course of the Trial, to temporarily interrupt or permanently discontinue the Trial intervention if it is deemed that continuation would be detrimental to, or not in the best interest of the participant.

Similarly, the Sponsor, CA/EC can decide to halt or prematurely terminate the Trial when new information becomes available whereby the rights, safety and well-being of Trial participants can no longer be assured, when de integrity of the Trial has been compromised, or when the scientific value of the Trial becomes obsolete and/or unjustifiable.

Circumstances requiring premature treatment interruption or discontinuation of the Trial, include but are not limited to:

- Safety concerns that are directly related to the intervention or unacceptable intolerability
- Trial participation while in violation of the inclusion and/or exclusion criteria
- Pregnancy

In any such case of early Trial termination and/or treatment interruption/discontinuation, the Investigator will continue to closely monitor the participant's condition and ensure adequate medical care and follow-up.

5 Trial product of interest

Food supplement (& company brand name)	Used within Indication? (Y or N)	Route of administration (po,sc,iv,)	Dose/dosage and units
deltaG Ketone	Not applicable	Enteral (gastric tube)	25g / 50g / 75g

DeltaG Ketones are commercially available as a soluble food supplement (called 'deltaG Ketone Performance'). We will be using pure deltaG Ketone ester as ketone supplement (100% R-3-hydroxybutyl-R-3-hydroxybutanoate, $C_8H_{16}O_4$). This ketone product has been developed at the university of Oxford and was shown to be safe and efficacious in healthy human volunteers [17]. Since 2008, deltaG has been the subject of a wide range of scientific safety studies that led to a Generally Recognized as Safe (GRAS) designation and a U.S. FDA notification. This supplement is also currently being investigated in patients with type I diabetes [18], in patients with type 2 diabetes and heart failure [19] and in a KU Leuven trial with athletes [20]. The food supplement will be delivered to us by deltaG.

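### Section 7.2 makes the 48-hour completers the primary set without exempting safety and tolerability, no all-dosed set is named for the escalation decision, and the replacement rules in 2.4 and 7.1/7.2 conflict

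*Protocol*

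**What the plan says.** All references are to the protocol.

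- **Analysis set (7.2).** The study "will continue until 16 participants per tested dose completed the 48h study period. This is the primary analysis (per-protocol-analysis". No endpoint is exempted and no other primary set is named.
- **Non-completers (7.2).** "Data from patients with a shorter study period will be analysed in as a sensitivity analysis", whose stated aim is to confirm that the partial results agree with the primary data. On missing values: "Imputation of missing data would not be accurate due to the small data set".
- **Reasons to stop (4.4).** The circumstances that call for interruption or discontinuation include "Safety concerns that are directly related to the intervention or unacceptable intolerability". After such a stop, "the Investigator will continue to closely monitor the participant's condition and ensure adequate medical care and follow-up".
- **Escalation (2.4).** After the 25 g cohort: "Next, we will assess the primary and secondary endpoints in this cohort of patients". The next dose is tested only if the current one proves safe without being effective. The secondary endpoints in 2.3 include ketoacidosis, severe hypoglycaemia and intolerance.
- **Replacement (2.4).** When a patient cannot complete the 48 hours "and this is not related to safety concerns that are directly attributed to the intervention, an extra patient will be included".
- **Target number (7.1).** 16 patients completing the study period per dose, with no exception for safety losses.

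**The concern.** A completer set suits a paired comparison, which needs both study days. It is a poor basis for judging safety when harm or intolerance can itself prevent completion. The patients who matter most to the question whether a dose is safe are the likeliest to fall outside the set that 7.2 calls primary. The sensitivity analysis does not make up for this. It looks for agreement with the completers, whereas patients who stopped because of the product are expected to differ from them.

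What is at stake is the step from 25 g to 50 g and from 50 g to 75 g. If 7.2 is followed as worded, the events behind that step are under-counted in the primary results.

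The second problem is a direct conflict. After one loss to an intervention-attributed safety concern, the team cannot both decline to replace the patient (2.4) and continue until 16 have completed (7.1, 7.2).

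**Working it through.** **1. The plan's own sample size.** Inputs from 7.1: increase 0.22 mM, SD of the within-patient difference 0.28 mM, paired t-test, 95% certainty, 80% power. I took 95% certainty to mean two-sided alpha 0.05.

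Effect size d = 0.22/0.28 = 0.786, as stated. Power comes from the noncentral t distribution with n − 1 degrees of freedom and noncentrality d√n. The smallest n reaching 80% is 15 (80.8%); n = 16 gives 83.6%. The stated 16 therefore reproduces, plausibly as 15 rounded up to 8 per sequence. The sample size is not in error.

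**2. If 2.4 governs (safety losses not replaced).** With 16 enrolled and k lost:

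| k | evaluable n | d√n | power |
|---|---|---|---|
| 0 | 16 | 3.14 | 83.6% |
| 1 | 15 | 3.04 | 80.8% |
| 2 | 14 | 2.94 | 77.6% |
| 3 | 13 | 2.83 | 74.0% |
| 4 | 12 | 2.72 | 69.9% |

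The stated 80% survives one loss but not two. These figures are for the paired test that 7.1 describes, a difference from zero.

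**3. If 7.1 and 7.2 govern (enrol until 16 complete).** The protocol gives no stop rate, so k is an assumption. With k safety or intolerance stops, all non-completers and all replaced, 16 + k patients are dosed:

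| k | stop rate among all dosed | of these, in the primary set |
|---|---|---|
| 1 | 1/17 = 5.9% | none |
| 2 | 2/18 = 11.1% | none |
| 3 | 3/19 = 15.8% | none |
| 4 | 4/20 = 20.0% | none |

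For a per-patient stop probability q, the chance of at least one stop before 16 completers is 1 − (1 − q)^16: 56% at q = 5%, 81% at 10%, 97% at 20%.

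Steps 2 and 3 are alternatives under opposite replacement rules. They must not be added together.

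**4. The replacement wording side by side.** The exception in 2.4 covers only safety concerns attributed to the intervention. Section 4.4 lists unacceptable intolerability as a separate item, while the synopsis tags intolerance as both safety and tolerability. Whether a patient stopped for vomiting is replaced is therefore unclear even within 2.4.

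**The case against.** The best defence is that 7.2 describes concentration-derived variables compared by paired tests, so its per-protocol label may be meant for those alone. No sentence there describes how ketoacidosis, hypoglycaemia or intolerance will be analysed, and a safety set is commonly defined in the SAP, which is not at hand. This has some force. But the protocol does more than stay silent: it labels completers as the primary analysis without restriction, and the conflict over replacement lies wholly within the protocol.

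Several stronger readings are tempting, and the protocol does not support them:

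- *The worst cases are excluded by design.* They are not. Shorter-period patients are analysed, though in a secondary place. Adverse reactions go into the eCRF (6.3, 8.2), and all deaths until 48 hours after the study period are reported (6.4).
- *The escalation decision uses completers only.* Section 2.4 refers to the cohort of patients without saying which set it means. Its lack of replacement for safety losses even suggests that they stay in the cohort. The defect is that the set is unstated.
- *Stopping treatment makes a patient a non-completer.* This is likely in practice, but it is nowhere stated. Section 4.4 allows temporary interruption and continues monitoring.
- *The plan would report 0/16 intolerance.* If stoppers are defined as non-completers, zero stops among completers is true by construction. The endpoint in 2.3 is intolerance, not stopping, and completers can have it.
- *The completer set is wrong for efficacy too.* Time within range is also a primary outcome variable, and it, the area under the curve and the half-life draw on the later samples. Changing that set would be a preference, not a correction.

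The power loss is also modest, and two safety stops attributed to the product would themselves bear on whether the dose is safe.

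**Conclusion.** The point holds in limited form, in two parts.

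First, the only primary set in the protocol is the 48-hour completers. Safety and tolerability are not exempted, and no all-dosed set is named for the judgement that a dose is safe. Read literally, patients who stop because of the product and do not complete are left out of the primary results. For an assumed 1 to 4 replaced stops, that hides a stop rate of 5.9% to 20.0% from the primary set. This rests on the assumed number of stops and on stopping leading to non-completion.

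Second, 2.4 contradicts 7.1 and 7.2 on patients lost to intervention-attributed safety concerns. If they are not replaced, power is 80.8% after one loss and 77.6% after two, against the stated 80%. The conflict itself needs no assumption.

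Both should be settled before the first escalation decision.

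**What to change.** - **7.2, safety set.** State that all safety and tolerability endpoints are summarised over every patient who received at least one bolus, by product received. A patient dosed on one day only then counts for that product alone.
- **2.4, escalation.** State that the assessment of whether a dose is safe uses this set.
- **7.2, efficacy set.** Keep the 48-hour completers for the paired 3-hydroxybutyrate analysis, and limit the per-protocol label to it.
- **2.4, 7.1 and 7.2, replacement.** Reconcile these into one rule. Say whether a stop for intolerance falls under the safety exception, whether a patient who stops treatment but stays under observation counts as a completer, and that replaced patients remain in the safety set.

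The cost is protocol wording only. Adverse reactions and the number of administration cycles are already recorded (8.2). After consent is withdrawn no new data are collected (4.1), so those patients contribute up to that point. If the replacement rule chosen leaves fewer than 16 completers, 7.1 should give the power for the reduced number.
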